**Table 2. Reporting Cutoffs for Clinical/Safety endpoints**

Visit	Reporting Cutoff Days	Lower Limit of the Reporting Window (days post-index procedure)
30 days	30 days post-index procedure	Days to last contact: 23
6-month	180 days post-index procedure	Days to last contact: 150
12-month	360 days post-index procedure	Days to last contact: 330
24-month	720 days post-index procedure	Days to last contact: 690
36-month	1080 days post-index procedure	Days to last contact: 1050

Other AE/SAEs that are recorded during the study will be reported on the standard safety population, i.e. all included subjects.

For 30-day primary safety endpoint

The components of the 30-day MAE composite endpoint include:

- All-cause death occurring post-procedure
- Clinically significant (i.e. symptomatic, confirmed by CT pulmonary angiography) pulmonary embolism
- Major bleeding complication (procedural)
- Stent thrombosis confirmed by imaging as assessed by core laboratory
- Stent migration confirmed by imaging as assessed by core laboratory

The following Table 3 specifies how individual component events are determined:

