2.0 02/MA R/2021	
 
Administrative updates including tense corrections at this timpoint in the study.
 
Updated Section "1 Version History" for ISO 14155:2020 compliance. Additional columns are marked as 'N/A' in previous CIP versions.
 
Added 'Post-Approval Study – PAS' and 'Premarket approval application – PMA' to Section "3. Glossary".
 
Section "4 Synopsis" updated 'Title' and 'Clinical Study Type' per PMA Approval Order. Added PMA approval status to 'Indication under investigation' and 'Product Status'. Added the post-approval primary objective to evaluate freedom from target lesion revascularization at 36 months to 'Primary Objectives'. Updated 'Sample Size' to indicate 200 subjects were implanted and included in the study from 24 investigational sites and clarification that no new subjects are allowed in the study. Updated 'Number of sites' to reflect 24 sites participated. 'Statistics' text updated to outline the newly added primary endpoint to assess freedom from target lesion revascularization through 36 months will be characterized with descriptive statistics.
 
Added text to Section "5.2 Purpose" to outline current PMA approval status and update the post-approval study phase primary endpoint.
 
Updated Section "6.1 Primary Objectives" with the newly added post-approval study phase objective.
 
Added the post-approval study phase primary effectiveness endpoint (freedom from TLR through 36 months) to Section "6.3.1 Primary Endpoints"
 
Removed sub-categories 'acute success secondary endpoints' and 'late success secondary endpoints' from "Section 6.3.2 Secondary Endpoints".
 
	
Changes made to align with the Abre Venous Self-expanding Stent System Approval Order (P200026, 21/OCT/2020).
 
Updates made to align with ISO14155:2020
	N/A	
As a result of these changes the ABRE Study Adverse Event CRF will be updated to include the new ISO14155:2020 AE definitions.
	[name] / Senior Clinical Research Specialist

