**Table 9: Potential adverse events**

 
- Access failure
 
- Access site infection
 
- Allergic reaction to contrast medium or procedure medications
 
- Allergic reaction to nitinol or other device materials
 
- Arrhythmia
 
- AV fistula
 
- Bleeding
 
- Bruising
 
- Death
 
- Device breakage
 
- Device maldeployment
 
- Edema
 
	
 
- Fever
 
- Hematoma
 
- Hypotension, nausea, or other vasovagal response
 
- Infection
 
- Myocardial infarction
 
- Pain
 
- Pseudoaneurysm
 
- Pulmonary embolism
 
- Renal insufficiency/renal failure (new or worsening)
 
- Sepsis
 
- Stent fracture
 
- Stent malapposition
 
- Stent malposition
 
	
 
- Stent migration
 
- Stroke/paradoxical embolism/transient ischemic attack/intracerebral hemorrhage
 
- Tissue necrosis
 
- Transfusion reaction following blood transfusion for treatment of major bleeding
 
- Vessel damage, including perforation or rupture
 
- Venous occlusion/thrombosis, within or outside of stented segment
 

---	---	--

Additional risks for the subject due to participation in the study may include:

- Discomfort during the imaging scans
- Potential significant radiation exposure due to beam intensity and length of time of imaging, resulting in acute radiation injury as well as increased risk for physical and genetic defects to subjects.

The following measures will be implemented to minimize any risks to study subjects:

- Investigator and study personnel will be trained to the design of the Abre system, its application and preclinical results.
- Eligibility criteria and screening procedures will be followed to ensure that appropriate subjects are enrolled and included.
- Investigator will adhere to the Abre system Instructions For Use packaged with the device.
- The subjects will be carefully monitored throughout the study period.
- The investigator will evaluate the subject adverse events during the course of the study.
- Data submitted from the investigative centers will be monitored during the course of the study.
- Monitoring visits will be conducted to evaluate protocol compliance and data quality.

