#### 12.2.4 Requirements for Adverse Event Reporting

Adverse events and device deficiencies should be reported by the investigator to Medtronic as soon as possible after the event occurs, but no later than the timeframes listed in **Table 14** or local requirements, whichever is more stringent.

Reporting all adverse events is no longer required effective with this version of the CIP (v 2.0) as unrelated adverse events greater than 12-months post-procedure do not have clinical impact on the long-term analysis of the safety and effectiveness, the post-market clinical follow-up (PMCF), or clinical evaluation of the device. This is the rationale for deviating from ISO 14155:2020 (7.4). Adverse events related to the device and / or procedure will continue to be reported as well as adverse events with major adverse event (MAE) potential such as: any target limb revascularization, any signs or symptoms pulmonary embolism, any bleeding complication (procedural & post-procedural), stent migration, and stent thrombosis. Serious and unanticipated events are still required to be reported. Adverse events that were reported in the ABRE pivotal study phase that are currently ongoing, must be followed to the AE resolution.

In addition, investigators are obligated to report adverse events and device deficiencies in accordance with the requirements of their reviewing Ethics Board and local regulations.

Medtronic is obligated to report adverse events and device deficiencies that occur during this study to the Regulatory Authorities and Ethics Board as per local requirements.

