**Table 14: Required Timeframes for Adverse Event reporting by investigator to Medtronic**

Timeframe for Reporting	Event Type
Immediately, but no later than 72 hours of the investigator's / site's first knowledge of the event (or sooner if required by local regulation)	
 
• Adverse Device Effect (ADE) or Device Related Adverse Event
 
• Device Deficiency (DD)
 
• Device Deficiency that might have led to an SADE
 
• Serious Adverse Device Effect (SADE)
 
• Serious Adverse Event (SAE)
 
• Unanticipated Adverse Device Effect (UADE)
 
• Unanticipated Serious Adverse Device Effect (USADE)
 

In a timely manner from the investigator's / site's first knowledge of the event	Adverse Event (AE): effective with this version of the CIP (v2.0), only procedure and/or device-related AEs (including those already called out in the row above as ADEs), or AEs that may potentially be adjudicated as an MAE  , are required to be reported. 

 Any target limb revascularization, any signs or symptoms pulmonary embolism, any bleeding complication (procedural & post-procedural), stent migration, and stent thrombosis.

Unrelated AEs, in particular those greater than 12-months post-procedure do not have a clinical impact on the long-term analysis of the safety and effectiveness, the post-market clinical follow-up (PMCF), or clinical evaluation of the device, and is the rationale for deviating from ISO 14155:2020 (7.4).

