## **7.10 Safety Evaluation**

For adverse events (AEs), serious adverse events (SAEs), major adverse events (MAE) and Unanticipated Adverse Device Effects (UADEs) reporting, the primary analysis will be based on subject counts, not event counts. The subject counts and the percentages will be presented in tabular summaries of results. Reporting of laboratory finding will be reported descriptively.

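### CIP v2.0 ends reporting of unrelated non-serious AEs during year 3 for up to about 76% of subjects, but the SAP still gives all-AE percentages over all included subjects

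*SAP*

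**What the plan says.** SAP 7.10 covers AEs, SAEs, MAEs and UADEs and makes the subject the counting unit: "The subject counts and the percentages will be presented in tabular summaries of results". Below Table 2 in section 10.3.1 it sets the population for the rest: "Other AE/SAEs that are recorded during the study will be reported on the standard safety population, i.e. all included subjects". No end date, collection period or AE category qualifies either statement. The SAP's last content update was to CIP v1.4, and v4.0 is dated 14 February 2020.

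Protocol 12.2.4, in the version dated 2 March 2021, then changes what sites send: "Reporting all adverse events is no longer required effective with this version of the CIP (v 2.0". The same section keeps several categories: "Adverse events related to the device and / or procedure will continue to be reported", as do AEs with MAE potential, and "Serious and unanticipated events are still required to be reported". AEs already ongoing are followed to resolution. Table 14 repeats the rule and keeps device deficiencies reportable. Protocol sections 12.2.4 and 15.1 acknowledge the change as a departure from ISO 14155:2020 (7.4). Protocol section 14 was revised at the same time to add the 36-month TLR analysis, but its sentences on AE tabulation set no matching limit.

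**The concern.** One denominator, all included subjects, is applied to a numerator collected under two rules. The change falls on a calendar date while subjects entered over a year, so it reaches each subject at a different study day. Early subjects had complete reporting to 36 months and later ones did not. For unrelated non-serious AEs without MAE potential, an event that was no longer reportable is counted as no event.

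The post-approval phase exists to describe long-term safety and effectiveness. A reader of an all-AE percentage on 200 subjects would assume uniform collection to 36 months and would have no way to see that one category was curtailed.

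**Working it through.** The plan states no figure for this effect, so the check is date arithmetic.

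**Inputs from the documents.** First enrollment 19 December 2017 (Protocol synopsis). 200 subjects enrolled in 12 months (Protocol 7.1). CIP v2.0 dated 2 March 2021 (Protocol section 1). 36-month cutoff 36 × 30 = 1080 days (SAP 10.2, 10.3.1). Approval is required before a revision is implemented at a site (Protocol 16.10), so 2 March 2021 is the earliest possible date; the actual dates are not given.

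**Assumptions.** Even accrual over 365 days, with implantation taken at enrollment; implementation on the same date at all sites, from 2 March to 2 December 2021; no dropout; constant hazard for the affected category.

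**Study day at the change.** 19 December 2017 to 2 March 2021 is 1096 + 73 = 1169 days. A subject entering on accrual day t is at day 1169 − t, so the first is at 1169 and the last at 1169 − 365 = 804.

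**Share affected.** Reporting is curtailed if 1169 − t < 1080, that is t > 89. The share is (365 − 89)/365 = 276/365 = 75.6%, about 151 of 200.

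**Days lost.** Days lost = max(0, 1080 − study day at change), at most 276. The mean over all subjects is 276²/(2 × 365) = 104.4 days: 104.4/1080 = 9.7% of 36-month person-time and 104.4/360 = 29% of year 3.

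| v2.0 in force | First / last subject at day | Share affected | Mean days lost | Share of 1080 days |
|---|---|---|---|---|
| 2 Mar 2021 | 1169 / 804 | 75.6% | 104.4 | 9.7% |
| 2 Jun 2021 | 1261 / 896 | 50.4% | 46.4 | 4.3% |
| 2 Sep 2021 | 1353 / 988 | 25.2% | 11.6 | 1.1% |
| 2 Dec 2021 | 1444 / 1079 | 0.3% | 0.0 | 0.0% |

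**Effect on the SAP's own measure.** The SAP reports a cumulative subject percentage, not person-time. For a true 36-month percentage p, the hazard is h = −ln(1 − p)/1080. The observed value is the average over t of 1 − exp(−h × min(study day at change, 1080)).

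| True p | Observed, 2 Mar (relative loss) | Observed, 2 Jun | Observed, 2 Sep |
|---|---|---|---|
| 10% | 9.1% (9.2%) | 9.6% (4.1%) | 9.9% (1.0%) |
| 20% | 18.2% (8.8%) | 19.2% (3.9%) | 19.8% (1.0%) |
| 50% | 46.4% (7.1%) | 48.5% (3.1%) | 49.6% (0.8%) |
| 80% | 76.4% (4.5%) | 78.5% (1.9%) | 79.6% (0.5%) |

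These losses apply to the curtailed category. An all-AE total with the same true percentage loses less, because its other components are still collected.

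**Sensitivity.** If implantation ran up to 30 days later (395 days), the last subject is at day 774, 77.5% are affected and the mean loss is 118.5 days (11.0% of 1080). The relative loss for true rates of 10–80% is then 5.2–10.5% with immediate effect and 0.8–1.7% after six months.

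**Day 720.** In both variants the last subject was past day 720, and past day 750, the end of the 24-month visit window, on 2 March 2021.

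**The case against.** The strongest reply is that the affected category is the least informative one. SAEs, related AEs, MAE-potential events and unanticipated effects continue, and the phase is descriptive with no success criterion (Protocol 14.5). The restriction is disclosed in the protocol with its rationale. SAP 7.12 and Protocol section 14 require analysis changes to be documented in the study report. All of this stands, and it limits the size of the point. It does not supply a rule for the table: an argument for not collecting certain events is not an argument for dividing a partly collected count by all included subjects.

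It is also fair that person-time shares (9.7%, or 29% of year 3) overstate the effect on a cumulative percentage, because a subject with an earlier AE is already counted. It is equally fair that site approval delays shrink it towards zero. One consideration runs the other way. Table 14 counts from the site's first knowledge, so an event that began before v2.0 but was learned of at a later visit may also go unreported. That is an inference from the text, and the documents give no way to size it.

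A reader might infer that the AE output will show a fall in year 3. The SAP plans no year-by-year AE table, nor a separately named 36-month AE rate; it tabulates AEs recorded during a study that runs to 36 months.

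A reader might also infer that target-limb DVT escapes reporting, because Table 9 lists "Venous occlusion/thrombosis, within or outside of stented segment" as a risk while Table 14 footnote 1 names only: "Any target limb revascularization, any signs or symptoms pulmonary embolism, any bleeding complication (procedural & post-procedural), stent migration, and stent thrombosis". The documents do not support widening that list. The footnote explains which events could be adjudicated as an MAE, and thrombosis outside the stent is not an MAE component (Protocol 6.3.2). Occlusion of the stented segment already falls under stent thrombosis (Protocol Appendix B). Section 12.2.4 introduces its own list as examples. A thrombosis that is serious or judged related remains reportable, and sites must still document AEs in the medical record (Protocol 12.2.1).

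**Conclusion.** The point holds in a limited form. As written, the SAP mixes full and curtailed collection under one denominator for unrelated non-serious AEs without MAE potential, and for any all-AE total that includes them. The understatement is about 4–9% relative (true 36-month percentages of 10–80%) if v2.0 applied everywhere on 2 March 2021. It is 2–4% with three months' delay, about 1% or less with six, and essentially nil with nine. This rests on even accrual over 12 months, a constant hazard and no dropout.

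It would be wrong to conclude that AE rates in general are understated. SAE, MAE, TLR, UADE and device- or procedure-related AE rates are collected under one rule throughout. The 30-day and 12-month primary endpoints were complete for every subject before the change. This is a modest, correctable defect in a descriptive table.

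**What to change.** Amend SAP 7.10 and 10.3.1 as follows.

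- Count unrelated non-serious AEs, and any all-AE total, only up to the date CIP v2.0 was implemented at the subject's site. Report them with a time-based denominator or a Kaplan-Meier estimate censored at that date. Truncating the count while still dividing by all included subjects would leave the understatement in place.
- Alternatively, give the all-AE percentage only to day 720, which every subject reached under full reporting. This is simpler but discards more: with immediate effect, 360 − 104 = 256 days per subject of fully collected year-3 data (71%), and after a six-month delay 360 − 11.6 = 348 days (97%).
- Tabulate through 36 months only the categories reportable throughout: SAEs, device- or procedure-related AEs, UADEs, device deficiencies, adjudicated MAEs and TLR.
- State in the table that collection changed with CIP v2.0, and from when.

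No change to the MAE-potential list is needed. The cost is SAP wording and one implementation date per site in the analysis data. The downside is an all-AE table with shorter or variable follow-up. No extra data collection from subjects is required.

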**Table 3. Individual Component Event Determination For 30-Day Safety Endpoint**

Primary Safety Endpoint Component Events	Data Source	Event Failure	Individual Endpoint Derivation Rules	Composite Endpoint Derivation Rules
All-cause death	CEC	Event within 30 days post-index procedure by CEC adjudication	Numerator: event-specific, e.g. number of subjects with all-cause death within 30-day post index procedure, will be the numerator for 30-day all-cause death event rate calculation; Denominator: event specific denominator includes any subjects with the event, or subjects had no event but had at least 23-day of clinical follow-up	Numerator: number of subjects with at least one of these five events within 30 days post-index procedure; Denominator: evaluable subjects – any subjects with at least one of these five events, or subjects had none of these five events but had at least 23-day of clinical follow-up
Clinically significant pulmonary embolism	CEC			
Major bleeding complication (procedural)	CEC			
Stent thrombosis	Imaging-Confirmed	Stent thrombosis or migration within 30 days post index-procedure, confirmed by Venogram imaging		
Stent migration	Imaging-Confirmed			

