#### **Primary safety endpoint**

The primary safety endpoint of this study will be the incidence of composite Major Adverse Events (MAE) at 30 days following stenting of an obstruction in the iliofemoral venous segment. MAEs will be adjudicated by a Clinical Events Committee (CEC), except for stent thrombosis and stent migration as they are confirmed by core laboratory.

The components of the 30-day MAE composite include:

- All-cause death occurring post-procedure
- Clinically significant (i.e. symptomatic, confirmed by CT pulmonary angiography) pulmonary embolism
- Major bleeding complication (procedural)
- Stent thrombosis confirmed by imaging as assessed by core laboratory
- Stent migration confirmed by imaging as assessed by core laboratory

Note: Migration excludes stent dislodgement at the index procedure as may occur with under-sizing of a stent.

---

All subjects will undergo DUS assessments for determination of patency.

An additional venogram must be performed when:

(1) DUS assessment is suggestive of ≥50% restenosis or occlusion per investigator assessment, or  
(2) when DUS is non-diagnostic or suboptimal such as when a patient is obese (e.g. with a BMI >40), or  
(3) is clinically required, or in other words when the patient is having symptoms of venous disease in the target limb requiring a venogram.

All DUS and venographic imaging examinations will be analyzed by respective independent core laboratories.

Clinically driven is defined as the recurrence of symptoms present at baseline or the onset of new symptoms including, but not limited to venous pain, swelling, dermatitis, or ulceration related to the target limb.

Clinically driven target lesion revascularization will be adjudicated by the CEC based on core laboratory adjudicated imaging data and relevant clinical information provided by the site.

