Stent migration	
Stent migration (as part of primary safety and secondary MAE endpoints): position change of a properly sized venous stent observed with an imaging modality, with displacement of the stent outside of the intended treatment segment after the conclusion of the index procedure, as determined with regard to a reference anatomic structure.
 
Delayed stent migration (as part of secondary endpoint): position change of a venous stent observed with an imaging modality > 1 cm from its original location at the conclusion of the index procedure, as determined with regard to a reference anatomic structure.
 
Stent migration occurs following the proper deployment of a venous stent after the index procedure (i.e. stent movement or dislodgement during the index procedure will not be noted as stent migration).

Stent thrombosis	
Occlusion of the stented venous segment occurring at any time following stent placement.
 
Stent thrombosis may be diagnosed by Duplex Ultrasound. It needs to be confirmed by venogram or IVUS.

Thrombosis	
A total occlusion due to thrombus formation as confirmed by sudden onset of symptoms and documented by DUS and venogram and/or IVUS at the target vessel.

Vein compression syndrome	
A condition in which compression of the common iliac venous outflow tract of the left lower extremity may cause discomfort, swelling, pain, or blood clots

	(deep vein thrombosis) in the iliofemoral vein (also known as the May-Thurner syndrome).
Venous occlusive disease	Any pathologic process that occurs from underlying stenosis or occlusion of the veins.

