## 7.9.2 Primary Safety Endpoint

The primary safety endpoint of this study will be the incidence of composite Major Adverse Events (MAE) at 30 days following stenting of an obstruction in the iliofemoral venous segment. MAEs will be adjudicated by a Clinical Events Committee (CEC), except for stent thrombosis and stent migration as they are confirmed by core laboratory.

The components of the 30-day MAE composite include:

- All-cause death occurring post-procedure
- Clinically significant (i.e. symptomatic, confirmed by CT pulmonary angiography) pulmonary embolism
- Major bleeding complication (procedural)
- Stent thrombosis confirmed by imaging as assessed by core laboratory
- Stent migration confirmed by imaging as assessed by core laboratory

Note: Migration excludes stent dislodgement at the index procedure as may occur with under-sizing of a stent.

More details of the reporting rules are used to determine this endpoint can be found in section 10.3.1.

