### 7.9.2.2 Statistical Method

The primary safety failure rate is calculated as the number of subjects who had a major adverse event within 30 days divided by the number of evaluable subjects who had enough follow up (at least 23 days for 30-day visit) plus any subjects who had a major adverse event within 30 days. Primary safety failure rate and the exact one-sided 97.5% upper confidence limit (UCL) will be reported. The primary safety objective will be met if the exact one-sided 97.5% UCL is below 12.5%.

For the primary safety endpoint, subjects will be included in the analysis and considered evaluable if:

- (a) the subject experiences at least one of the primary safety composite events within 30 days, or
- (b) stent migration and/or stent thrombosis within 30 days confirmed by imaging as assessed by core laboratory, or
- (c) the subject has at least 23 days of clinical follow up without an event in the primary safety endpoint.

Tiping point analysis for primary safety endpoint as sensitivity analysis is mentioned in section 7.4.2.

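### SAP Table 3 counts 30-day stent thrombosis and migration only on venogram, narrower than the endpoint definition; a migration seen on another modality would be scored event-free

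*SAP*

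**What the plan says.** SAP 10.3.1 introduces the component rules with "The following Table 3 specifies how individual component events are determined". For both stent components, the event-failure column of Table 3 then reads "Stent thrombosis or migration within 30 days post index-procedure, confirmed by Venogram imaging".

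Other passages are broader:

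- **SAP 7.9.2**, the component list in SAP 10.3.1 just above Table 3, and **protocol 6.3.1** name no modality: "Stent thrombosis confirmed by imaging as assessed by core laboratory" and "Stent migration confirmed by imaging as assessed by core laboratory".
- **SAP 7.9.2.2**, evaluability item (b), makes a subject evaluable on "stent migration and/or stent thrombosis within 30 days confirmed by imaging as assessed by core laboratory".
- **Protocol Appendix B**, thrombosis: "Stent thrombosis may be diagnosed by Duplex Ultrasound. It needs to be confirmed by venogram or IVUS".
- **Protocol Appendix B**, migration as used in the safety endpoint: "position change of a properly sized venous stent observed with an imaging modality".

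A subject with no counted event enters the denominator as a non-event if "the subject has at least 23 days of clinical follow up without an event in the primary safety endpoint". Neither this item nor Table 3 adds an imaging condition.

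On imaging, protocol Table 7 and section 10.7 schedule duplex ultrasound (DUS) for everyone at 30 days and X-ray for the first 30 subjects, the latter to look for fracture. No venogram is scheduled. Under protocol 10.12.6.1 a venogram is mandatory at the index procedure, at re-intervention in the target vein, and at 12 months under stated conditions. At other times it is left to the investigator.

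**The concern.** The operative derivation table and the endpoint definition can give different event counts from the same data. The difference runs one way: Table 3 can only remove events from the numerator of a test that passes when the upper limit is below 12.5%. The subject stays in the denominator. Under SAP 7.9.2.2(b) a core-laboratory migration can even be what makes a subject evaluable, while Table 3 does not count it.

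Nothing else in the plan catches this. The tipping-point analysis (SAP 7.4.2) addresses missing or unknown outcomes, and these subjects are evaluable non-events. Double programming (SAP 8) does not settle which text governs.

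**Working it through.** **1. What Table 3 removes, by component.**

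- *Migration.* Appendix B and SAP 7.9.2 accept a migration seen on any modality and assessed by the core laboratory. Table 3 drops it unless a venogram was also done. At 30 days the scheduled non-venogram source that best fits is the X-ray in the first 30 subjects; for delayed migration SAP 10.3.2 names X-ray or venography. A migration that leads to re-intervention gets a mandatory venogram, so the exposed cases are those managed without one.
- *Thrombosis.* Against Appendix B, Table 3 loses only IVUS confirmation. After the index procedure IVUS is required only at re-intervention (protocol 10.12.6.3), where a venogram is required as well (10.12.6.1). The loss is therefore nearly empty. A DUS-only occlusion is already excluded by Appendix B.

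**2. Reproducing the design.** Inputs from SAP 6.3: n=193, goal 12.5%, expected rate 5.6%, reject if 15 or fewer events.

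- Type I error = P(X≤15 | 193, 0.125) = 0.0249; the SAP states 0.0249.
- Power = P(X≤15 | 193, 0.056) = 0.9233; the SAP states 0.9233.

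**3. How much one event matters.** Exact one-sided 97.5% upper limits:

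| n | 15 events | 16 events |
|---|---|---|
| 193 | 12.49% (passes) | 13.11% (fails) |
| 200 | 12.07% (passes) | 12.67% (fails) |

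The limit is 15 at every n from 193 to 200. Sixteen events first pass at n=203 (12.48%), above the 200-subject maximum.

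**4. Illustrative size of the migration loss.** The documents do not say how many migrations would lack a venogram. Assume that:

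- migration keeps its literature share of events, 1.4/5.6 = 0.25 (weighted averages, protocol Appendix A Table IV);
- only migrations on the 30-day X-rays of the first 30 subjects are lost;
- none of those has a venogram.

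At a true rate of 12.5%, the counted rate in those 30 is 0.125 × (1 − 0.25) = 0.09375, and it stays 0.125 in the rest. The chance of passing is P(X₁+X₂ ≤ 15):

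- n=193: X₁~Bin(30, 0.09375), X₂~Bin(163, 0.125) gives 0.039, against 0.025 with no loss.
- n=200: X₂~Bin(170, 0.125) gives 0.026, against 0.016 with no loss.

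At the literature migration rate, the expected number of migrations among those 30 subjects is 30 × 0.014 = 0.42.

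**The case against.** The best defence is that the mismatch has little effect. The data-source column of Table 3 says only that the event is imaging-confirmed, and the list just above it carries the broad definition, so the venogram wording may be shorthand. For thrombosis, Table 3 is close to Appendix B. Re-intervention brings a venogram. Expected losses are below one event at literature rates. With 200 subjects implanted, n may be near 200, where the illustrative type I error is about nominal. All of this stands as to size. It does not remove the contradiction, because SAP 10.3.1 makes Table 3 the determining rule.

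A reader might infer something stronger: that duplex-detected occlusions are being dropped and the safety test is badly inflated. Thrombosis and migration together supply 2.9 + 1.4 = 4.3 of the 5.6 planning points (77%). If a quarter of all such events lacked a venogram, the counted rate at a true 12.5% would be 0.125 × (1 − 0.77 × 0.25) = 0.101, which passes with probability 0.17 at n=193. The documents do not support that reading. Appendix B requires venogram or IVUS to confirm a thrombosis, so an unconfirmed duplex finding is not an event under the protocol's own definition.

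Nor do they support treating event-free subjects without a readable 30-day image as unknown outcomes. Neither document makes imaging a condition of evaluability for a subject without an event.

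On timing, protocol 14.3(b) ties the stent components to the 30-day visit and 14.4.1 counts events before that visit, whose window runs to day 44 (protocol 10.7). The SAP's 30-day cutoff and earliest-event rule (10.3.1, Table 2) largely settle this, so it is an alignment matter only.

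Finally, the pivotal analysis has already gone to FDA (protocol 4 and 5.2). The rule therefore cannot be changed as if it were prospective.

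**Conclusion.** The contradiction is certain and lies in the operative rule for a primary endpoint. Its practical reach is stent migration seen by the core laboratory without a venogram, in a subject with at least 23 days of clinical follow-up and no other component event. For thrombosis the gap against Appendix B is nearly empty.

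The direction favours passing, and a result at the boundary could turn on one case. The likely effect is small: about 3.9% type I error at n=193 and 2.6% at n=200 under the stated X-ray assumptions. The documents give no rate for migrations found by discretionary IVUS, duplex or unscheduled X-ray, so these figures are illustrative, not a bound. The stated sample size and power are correct and are unaffected. This should be fixed, but it does not show that the safety conclusion is wrong.

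**What to change.** 1. In SAP Table 3, replace the venogram-only condition with the core-laboratory imaging definition of SAP 7.9.2, read with protocol Appendix B: venogram or IVUS for thrombosis, and the accepted modalities named for migration.
2. Align protocol 14.3(b) and 14.4.1 with the SAP's 30-day cutoff.
3. Because the pivotal analysis has been submitted, document the correction with its reason as a change to the planned analysis (SAP 7.12), and report the safety test recounted under the corrected rule.

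This costs wording and one recount from images the core laboratories already read. It adds no procedures, leaves the design power unchanged, and does not alter the primary evaluability rule.

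Optionally, add a supportive analysis, labelled post hoc, that counts core-laboratory DUS occlusions of the stented segment by the 30-day visit unless venogram or IVUS refutes them. Its downside is DUS false positives. If these added 0.5 or 1 percentage point to a true 5.6%, the chance of passing that analysis, P(X≤15), would fall from 0.923 to 0.867 or 0.793 at n=193, and from 0.903 to 0.836 or 0.751 at n=200. It should not replace the primary test.
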